3.1 Definitions

The following definitions apply:

- Baseline last observation collected prior to first administering of IMD.
- Change from baseline post-treatment assessment minus baseline assessment.
- Prior medication all medication taken within 10 days (whether continuing or not) prior to Day 0.
- Concomitant medication all medication taken from Day 0 (including medication taken immediately pre-injection and post-injection) until the Week 104 visit.
- Duration of adverse event (AE) stop date minus onset date + 1.
- Treatment emergent AE (TEAE) AE starting at the time point of first IMD dosing or thereafter.
- Local TEAEs TEAE occurring at the treatment area or just around the treatment area (≤ 2 cm from treatment area).
- Adverse device effect (ADE) AE related to IMD and/or study procedures as well as any AE related to a device deficiency.

3.2 Analysis variables

3.2.1 Performance variables

3.2.1.1 NLF-SRS grading of nasolabial folds

The severity of NLFs will be evaluated live by the investigator and on photographs by an independent reviewer using the NLF-SRS¹.

The scale is described in Table 1.

CROMA NLF-SRS grade	Description
0	None/minimal: No visible/minimal nasolabial folds
1	Mild: Shallow but visible nasolabial fold with a slight indentation
2	Moderate: Moderately deep nasolabial fold
3	Severe: Very deep nasolabial fold with prominent facial feature
4	Extreme: Extremely deep and long nasolabial fold with skin redundancy

 Table 1
 Nasolabial folds severity rating scale (NLF-SRS)

The left and right nasolabial fold are separately graded.

Page 13 of 21

3.2.1.2 GAIS

Aesthetic improvement will be evaluated by both the investigator and the subject, for each treatment location (right NLF, left NLF) separately, using the GAIS², a widely-used instrument presented in Table 2.

 Table 2
 Global Aesthetic Improvement Scale (GAIS)

3.2.1.3 Subject's satisfaction assessment

Subject's satisfaction with the treatment will be assessed using the FACE-Q questionnaire "Satisfaction with Outcome" scale³ in Table 3:

Table 3FACE-Q questionnaire

The results of the six items (a - f) will be summed up. If data is missing for less than three of the six items, the mean of the completed items will be inserted for the missing items. This raw scale summed score (from 1 to 24) will be converted into a satisfaction with outcome score (from 0 to 100) according the FACE-Q satisfaction via outcome conversion table³.

3.2.1.4 Pain assessment

The subjects will be asked to quantify the pain associated with IMD administration by means of a semi-quantitative 11 point Numeric Pain Rating Scale (NPRS)⁴, where 0 corresponds to no pain, and 10 to the worst pain imaginable. Pain intensity will be assessed immediately after completion of initial treatment and approximately 15 min thereafter.

Page 14 of 21

3.2.1.5 Assessment of aesthetic effect

The investigator will assess whether the aesthetic effect is still present in the subject. A liveassessment of the treated areas will be performed and the treated areas will be compared to the subject's photographs obtained at the Baseline Visit. The presence of the aesthetic effect will be recorded as either "Yes" or "No".

3.2.2 Safety variables

3.2.2.1 Medical history and demographic data

Medical history will be collected, covering relevant past medical history with particular reference to facial aesthetic or surgical procedures. Information on year of birth, gender and race will be collected as well.

3.2.2.2 Adverse events

All AEs will be assessed in terms of seriousness (yes/no), severity (mild/moderate/severe), relationship to the IMD or clinical investigation procedures (definite/probable/possible/unlikely/ not related), and outcome (resolved/ongoing/resolved with sequel ae/fatal/unknown). For details see CIP, section 14.4 "AE/SAE assessment".

3.2.2.3 Prior and concomitant medications

Prior medication is defined as all medication taken within 10 days (whether continuing or not) prior to Day 0.

Concomitant medication is defined as all medication taken from Day 0 (including medication taken immediately pre-injection and post-injection) until the Week 104 visit.

At each visit subjects are asked about any new medication taken or changes in current medication, as well as, about any aesthetic procedure applied in the area treated with the investigational device.

3.2.2.4 Pregnancy test

In females of childbearing potential, including women who are postmenopausal for less than 12 months, a urine pregnancy test will be performed using a dipstick test. The result will be recorded in the subject's medical record and the eCRF. This test must be done at each visit except visits 2 and 4 which will be performed by telephone communication approximately 24h post-treatment.

3.2.3 Pharmacokinetic and pharmacodynamic variables

Not applicable.

3.3 Analysis sets

All safety analyses will be based on the Safety analysis set, defined as all subjects who received the IMD.

The Intent-to-Treat (ITT) population is defined as all subjects who received the IMD and have at least one post-treatment assessment. The ITT population will be the primary analysis population for analyses of performance of the investigational device and of aesthetic effects in interim and in final analysis.

Page 15 of 21

The assignment of subjects to the safety analysis set and to the ITT population will be done prior to the interim analysis after Week 24.

A Per-Protocol (PP) population is defined to provide sensitivity analyses in the final analysis. The PP population comprises all subjects in the ITT population, who completed the Week 24 assessment without any major CIP deviations (i.e. CIP deviations that interfere with the performance evaluation or the aesthetic effect evaluation).

Subjects will be excluded from the PP population,

- who violated any inclusion/exclusion criteria during the course of the study;
- who's primary performance outcome measure, the ≥1-point improvement over Baseline on the NLF-SRS based on investigator's live assessment at Week 24 is missing, except it is a missing assessment for treatment related reason, e.g. discontinuation of assessments due to adverse events at least possibly related to IMD or due to lack of efficacy;
- who received any medication or procedure interfering with the performance or aesthetic effect evaluation at Week 24.

Prior to the final statistical analysis, other additional criteria may be added to the list to accommodate for unforeseen events that occurred during the conduct of the trial that result in noteworthy study protocol violations.

The assignment of subjects to the PP population will be finalized within a data review meeting for the final analysis.

3.4 Statistical methods

The final statistical analysis will be done after completion of the investigation by all subjects. The interim analysis will be done after all subjects have completed the Week 24 study procedures.

In general, collected data will be listed and descriptive statistics will be performed, with all repeating measurements being tabulated by visit.

For qualitative and discrete variables, the total number of observations, frequency and percentages of categories / scores will be calculated.

Quantitative and continuous variables will be described by declaring descriptive summary statistics (number of observations, the mean value, standard deviation, minimum, first quartile, median, third quartile, and maximum).

Two-sided 95% confidence intervals will be calculated assuming normal distribution, if not stated otherwise.

The primary and secondary performance analysis and the safety analysis will be done for each manufacturing site, C1 and HQ, separately and for the whole analysis population. The exploratory performance analysis will be done for the whole analysis population, ITT and PP respectively, only.

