#### 3.3 Justification for the clinical investigation

The current clinical investigation is designed to evaluate the performance of saypha® VOLUME Lidocaine for the correction of nasolabial folds using injection into the deep dermis or supraperiostal and to compare two different manufacturing sites.

In addition, this investigation should support the approval by obtaining clinical data on the performance and safety of saypha® VOLUME Lidocaine for the correction of nasolabial folds.

A prospective, non-comparative design was selected because it allows for the most efficient collection of clinical data on the investigational device, in a manner which is appropriate to address the purpose and objectives of the present investigation. In the absence of spontaneous improvement of nasolabial folds, it is reasonable to assume that the treatment effect can be adequately assessed by comparing the post-treatment observations versus baseline, eliminating the need for a control group. The randomization regarding manufacturing site, C1 and HQ, will be performed according the ratio 1:1 to present the results of the two manufacturing sites descriptively.

The primary performance endpoints are based on evaluation using a validated 5-point scale for assessment of severity of nasolabial folds, the Nasolabial Folds Severity Rating Scale (NLF-SRS), and is set at 24 weeks after administration of the device to address the minimum required durability of effect. Follow-up is extended a maximum up to 104 weeks, to get additional information on long-term effects and to evaluate the aesthetic outcome. Information on occurrence of pain will be primarily obtained by collection of AEs, with additional insight into pain intensity being obtained directly after the injection using a validated 11-point Numeric Pain Rating Scale (NRPS).

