#### 6.1.4 Exploratory performance endpoints

The primary and secondary performance endpoints will be evaluated within the subgroups defined by the injection device, needle and cannula, respectively.

The following endpoints will be assessed for the whole analysis population:

- The proportion of subjects with the NLF-SRS grade reduced by ≥2 point versus baseline at Week 4, Week 24, Week 36 and Week 52 and optional at Week 65, Week 78 and Week 104.
- The proportion of subjects with aesthetic improvement at Week 4, Week 24, Week 36 and week 52 and optional at Week 65, Week 78 and Week 104 as evaluated by the investigator using the Global Aesthetic Improvement Scale (GAIS).
- The proportion of subjects with aesthetic improvement at Week 4, Week 24, Week 36 and week 52 and optional at Week 65, Week 78 and Week 104 as evaluated by the subject using the Global Aesthetic Improvement Scale (GAIS).
- Subjects' satisfaction with aesthetic outcome of the treatment at Week 4, Week 24, Week 36 and week 52 and optional at Week 65, Week 78 and Week 104 as evaluated by the subject.
- The average pain intensity during and after the treatment, as evaluated by the subject using an 11point Numeric Pain Rating Scale (NPRS) immediately after the last injection and 15 min. thereafter, respectively.
- The proportion of subjects with the NLF-SRS grade reduced by ≥1 point versus baseline at Week 4, Week 24, Week 36 and week 52 and optional at Week 65, Week 78 and Week 104 as evaluated by the independent reviewer of photographs.
- Percentage of subjects having an aesthetic effect at Weeks 24, Week 36, Week 52 and optional at Week 65, Week 78 and Week 104 based on the investigator's life assessment.

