#### 7.4.1 *Performance endpoints*

As two facial folds of each subject will be considered, there are two measurements per subject for NLF-SRS. No great differences between the folds are expected, thus the mean of both measurements will be used for analyses. NLF-SRS grades per visit will be calculated as the mean of grades assigned to

the left and the right nasolabial fold, respectively. The absolute NLF-SRS change versus baseline will be computed by subtracting the value obtained on the corresponding visit from that obtained on Day 0 . Absolute NLF-SRS change from baseline will be summarized by the visit using descriptive statistics and additionally the 95% confidence intervals of the expected change from baseline will be given. In addition, the proportion (with two-sided 95% confidence intervals) of subjects with NLF-SRS improvement (i.e., reduction on both sides in NLF-SRS grades) of  $\geq$ 1, or  $\geq$ 2, respectively, will be calculated.

Individual GAIS grades, subjects' satisfaction with aesthetic outcome, and pain ratings will be summarized and tabulated by visit using descriptive statistics.

Summaries will be provided for the whole analysis population, as well as within each manufacturing site, C1 and HQ, separately.

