1.2.3 Exploratory performance endpoints

As exploratory endpoints the primary and secondary performance endpoints will be evaluated within the subgroups defined by the injection technique and device within each manufacturing site and for the whole analysis population:

- The proportion of subjects with the NLF-SRS grade reduced by ≥1 point versus baseline at Week 4, Week 24, Week 36, Week 52 and optional at Week 65, Week 78 and Week 104 by by injection technique (retrograde, bolus) and device (needle, cannula).
- The average change versus baseline in the NLF-SRS grade at Week 4, Week 24, Week 36, Week 52 and, optional at Week 65, Week 78 and Week 104 as evaluated by the investigator by injection technique (retrograde, bolus) and device (needle, cannula).

The following exploratory endpoints will be assessed for the whole analysis population only:

- The proportion of subjects with the NLF-SRS grade reduced by ≥2 point versus baseline at Week 4, Week 24, Week 36 and Week 52 and optional at Week 65, Week 78 and Week 104.
- The proportion of subjects with aesthetic improvement at Week 4, Week 24, Week 36, Week 52 and optional at Week 65, Week 78 and Week 104, as evaluated by the investigator using the Global Aesthetic Improvement Scale (GAIS)
- The proportion of subjects with aesthetic improvement at Week 4, Week 24, Week 36, Week 52 and optional at Week 65, Week 78 and Week 104, as evaluated by the subject using the Global Aesthetic Improvement Scale (GAIS)
- Subjects' satisfaction with aesthetic outcome of the treatment at Week 4, Week 24, Week 36, Week 52 and optional at Week 65, Week 78 and Week 104 using the Face-Q Satisfaction with outcome Scale as evaluated by the subject
- The pain intensity during and after the treatment, as evaluated by the subject using an 11point Numeric Pain Rating Scale (NPRS) immediately after the last injection and 15 min. thereafter, respectively
- The proportion of subjects with the NLF-SRS grade reduced by ≥1 point versus baseline at Week 4, Week 36, Week 52 and optional at Week 65, Week 78 and Week 104 as evaluated by the independent reviewer of photographs.

page 8 of 21

• The proportion of subjects having an aesthetic effect at Weeks 24, Week 36, Week 52 and optional at Week 65, Week 78 and Week 104 based on the investigator's life assessment.

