1.3 Modifications from the statistical section in the protocol

Not applicable.

2 Investigational plan

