• descriptive summary statistics for average change versus baseline in the NLF-SRS grade, evaluated by the investigator at Week 4, 24, 36, 52 and optional at Week 65, 78 and 104 after initial treatment,

Exploratory performance outcome measures

For exploratory performance outcome measures the following will be given for the whole analysis population:

- percentage of responders with a ≥2-point improvement over Baseline on the 5-point NLF SRS, based on investigator's live assessment at Week 4, 24, 36, 52 and optional at Week 65, 78 and 104 after initial treatment,
- percentage of subjects with aesthetic improvement using the 5-point GAIS (subjects who have been rated as "very much improved" or "much improved" or "improved"), based on investigator's assessment at Week 4, 24, 36, 52 and optional at Week 65, 78 and 104 after initial treatment, for each treatment location (right NLF, left NLF) separately and overall,
- percentage of subjects with aesthetic improvement using the 5-point GAIS (subjects who have been rated as "very much improved" or "much improved" or "improved"), based on subject's assessment at Week 4, 24, 36, 52 and optional at Week 65, 78 and 104 after initial treatment, for each treatment location (right NLF, left NLF) separately and overall,
- percentage of responders with a ≥1-point improvement over Baseline on the 5-point NLF SRS, based on evaluation by an independent reviewer of photographs for Week 4, 24, 36, 52 and optional at Week 65, 78 and 104 after initial treatment,
- descriptive summary statistics for extent of subject satisfaction with outcome of the treatment, as assessed by the Face-Q questionnaire "Satisfaction with Outcome" at Week 4, 24, 36, 52 and optional at Week 65, 78 and 104 after initial treatment,
- descriptive summary statistics for pain intensity, as evaluated by the subject using an 11point Numeric Pain Rating Scale (NPRS) immediately after the last injection and 15 min thereafter, at Day 0 and optional at Week 2.
- percentage of subjects having an aesthetic effect, based on the investigator's life assessment at Week 4, 24, 36, 52 and optional at Week 65, 78 and 104.

Subgroups by injection device and by injection technique for performance outcome measures For analyses by the injection device (needle, cannula) and by injection technique (retrograde,

bolus) the following will be given for the whole analysis population:

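### The protocol disagrees with itself on whether exploratory outcomes are tabulated by manufacturing site, and the SAP settles on pooled tables without recording the choice

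*SAP*

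**What the plan says.** **Protocol, pooled.** Section 6.1.4 introduces its list of exploratory endpoints with "The following endpoints will be assessed for the whole analysis population", and the synopsis endpoint list does the same. The list holds the ≥2-point response, GAIS by investigator and by subject, satisfaction, pain, the independent photo reading and the investigator's aesthetic-effect assessment. Sections 6.1.2 and 6.1.3, by contrast, set the primary and secondary endpoints by manufacturing site as well as overall.

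**Protocol, by site.** Section 7.4.1 covers NLF-SRS change and the ≥1- and ≥2-point responses, then says that GAIS, satisfaction and "pain ratings will be summarized and tabulated by visit using descriptive statistics". It closes without qualification: "Summaries will be provided for the whole analysis population, as well as within each manufacturing site, C1 and HQ, separately". The synopsis methods carry the same closing sentence.

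**SAP.** Section 1.2.3 adds a word that the protocol does not have: "The following exploratory endpoints will be assessed for the whole analysis population only". Section 3.4 repeats the restriction: "The exploratory performance analysis will be done for the whole analysis population, ITT and PP respectively, only". Section 3.4.3.2 places the by-site sentence directly after the confidence intervals for the ≥1- and ≥2-point responses, and then puts the ≥2-point response in a list headed "For exploratory performance outcome measures the following will be given for the whole analysis population". Section 1.3, headed "Modifications from the statistical section in the protocol", is answered as not applicable.

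**The concern.** Manufacturing site is the only randomised factor, and protocol 3.3 says that the randomisation serves to present the two sites' results descriptively. A pooled table of an exploratory outcome makes no use of it. A programmer working from these documents must also choose between contradictory instructions, most plainly for the ≥2-point response.

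At stake is whether a difference between the sites in GAIS, FACE-Q, NPRS scores or visible aesthetic effect could be seen in any table. The aesthetic-effect item bears on a stated objective, the duration of the effect (protocol 5.1). It can also affect follow-up: protocol 6.4.7 allows a subject's participation to end from Week 52 once the effect is gone, and missing data are not imputed (protocol 7.3). By-site NLF-SRS results after Week 52 may therefore come from subjects selected on an item that is itself shown only pooled.

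**Working it through.** **1. The texts side by side**

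| Outcome | Protocol 6.1.4 | Protocol 7.4.1 | SAP 1.2.3 and 3.4 | SAP 3.4.3.2 |
|---|---|---|---|---|
| ≥2-point response | whole population | named; by site and overall | pooled only | by site in the general text, whole population in the list |
| GAIS, both raters | whole population | named; by site and overall | pooled only | whole population |
| Satisfaction (FACE-Q) | whole population | named; by site and overall | pooled only | whole population |
| Pain (NPRS) | whole population | named; by site and overall | pooled only | whole population |
| Aesthetic effect, yes/no | whole population | not named; general closing sentence only | pooled only | whole population |

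The disagreement starts inside the protocol. The SAP follows 6.1.4 rather than 7.4.1. Since 7.4.1 belongs to the protocol's statistical section, SAP 1.3 should have recorded the choice.

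A related mismatch concerns the subgroups. SAP 1.2.3 sets the injection-technique and injection-device analyses by manufacturing site and overall, while SAP 3.4 and 3.4.3.2 give them for the whole population.

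**2. What is already shown by site**

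- The ≥1-point response and mean NLF-SRS change, at all visits from Week 4 to Week 52 and the optional visits to Week 104 (SAP 1.2.1, 1.2.2, 3.4.3.2).
- Adverse events (protocol 7.4.2, SAP 3.4.4.2). These include pain that is reported spontaneously or graded 4 or more (protocol 6.4.8).

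Without a by-site table are both GAIS ratings, FACE-Q, the NPRS scores, the aesthetic-effect proportion and, depending on which sentence is followed, the ≥2-point response.

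**3. Precision of the added columns**

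The plan's own figure comes first (protocol 7.1): n = 50, p = 0.9, normal approximation, two-sided 95%.

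0.9 ± 1.96 × √(0.9 × 0.1 / 50) = 0.9 ± 0.0832 = 0.8168 to 0.9832

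This reproduces the stated [0.817; 0.983].

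The same formula, 1.96 × √(p(1 − p)/n), applies to an exploratory proportion. The documents give no rates for these outcomes, so the range of p is assumed. The n of 50 per site and 100 pooled are the Week 24 targets.

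| Assumed rate | By site, n = 50 | Pooled, n = 100 |
|---|---|---|
| 10% or 90% | ±8.3 points | ±5.9 points |
| 25% or 75% | ±12.0 points | ±8.5 points |
| 50% | ±13.9 points | ±9.8 points |

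**4. What pooling can hide (assumed rates)**

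Suppose an aesthetic effect is present in 35% at one site and 65% at the other.

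- Pooled: (35 + 65)/2 = 50%; 50 ± 9.8 gives 40.2% to 59.8%.
- By site: 1.96 × √(0.35 × 0.65 / 50) = 0.132, giving 21.8% to 48.2% and 51.8% to 78.2%.

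The by-site intervals do not overlap, and the pooled row gives no sign of the gap. This shows what is possible; it does not predict a difference.

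**The case against.** The strongest reply is that the SAP follows the more specific text. The protocol sets primary and secondary endpoints by site and introduces the exploratory list differently, so pooling looks like a deliberate hierarchy, while the by-site sentence in 7.4.1 is a general closing line. The study is descriptive with no hypothesis tests (protocol 5.2), and by-site primary, secondary and safety results arguably already serve the purpose of the randomisation. This stands as a reason for modest weight, and it makes pooled-only reporting a position the sponsor could defend. It does not explain why 7.4.1 states the by-site promise straight after naming GAIS, satisfaction and pain, or why SAP 1.3 is silent.

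Three stronger readings are tempting, and the documents do not support them:

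- *The SAP simply departs from the protocol.* It follows one of two conflicting protocol passages. For the aesthetic effect, the by-site promise rests only on the general closing sentences in 7.4.1 and the synopsis methods.
- *Differences between sites in durability or pain would appear in no table.* NLF-SRS response and change by site show persistence of correction, and pain recorded as an adverse event is summarised by site. The aesthetic-effect item is a proportion at each visit, not a measure of duration.
- *The trial is meant to test one site against the other.* Protocol 3.3 does say "to compare two different manufacturing sites", but the same section calls the design non-comparative and the presentation descriptive. By-site columns would meet that purpose; a formal contrast is not promised.

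**Conclusion.** The point holds as a conflict to be reconciled and a gap in by-site reporting of exploratory outcomes. Both GAIS ratings, FACE-Q, NPRS scores and the aesthetic-effect proportion have no by-site table, and the ≥2-point response may have none. No primary, secondary or safety result changes, and neither the sample size nor the interval in protocol 7.1 is affected.

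The precision figures rest on assumed rates and on 50 evaluable subjects per site. With fewer subjects at later visits the intervals would be wider. Even at ±8 to ±14 points, by-site summaries give descriptive information that pooled ones cannot.

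**What to change.** - **SAP 3.4:** replace the restricting sentence with: *Exploratory performance outcomes will be summarised by manufacturing site (C1, HQ) and for the whole analysis population, for ITT and PP respectively.* This keeps the analysis sets specified.
- **SAP 1.2.3 and the exploratory list in 3.4.3.2:** align both for the ≥2-point response, both GAIS ratings, FACE-Q, NPRS and the aesthetic effect. The new sentence would also reach the photo reading and the technique and device subgroups, so state explicitly how each of those is presented.
- **Protocol:** reconcile 6.1.4 and the synopsis endpoint list with 7.4.1 and the synopsis methods.
- **SAP 1.3:** correct the entry. If the sponsor prefers pooled tables, say so there with the reason, and bring protocol 7.4.1 and the synopsis methods into line.

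The cost is a wording change and two extra columns per table, with no new data, subjects or visits. The downside is more descriptive tables, with by-site intervals wider than the pooled ones.
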